1. PROTOCOL SYNOPSIS

Name of Sponsor/Company

CSPC Ouyi Pharmaceutical Co., Ltd, a subsidiary company within CSPC Pharmaceutical Group, Ltd (CSPC)

Title of Study

A Randomized, Open-label, Single-Dose, Two-Way Crossover Study to Assess the Relative Bioavailability of 5 mg of Levamlodipine Maleate Tablets versus 10 mg of Amlodipine Besylate Tablet (NORVASC[®] from Pfizer Inc.) in Healthy Subjects Followed by a Phase to Study Food Effect on the PK Profile of Levamlodipine

Phase of Development

Phase 1

Investigational Product, Dosage and Mode of Administration

Levamlodipine Maleate Tablet is a new investigational drug for the treatment of hypertension and Coronary Artery Disease (CAD) chronic stable angina. Levamlodipine is the pharmacologically active isomer in amlodipine, which presents in amlodipine as a 1:1 mixture with the (R)amlodipine. The to-be-marketed dosage strengths planned in the US are 1.25, 2.5 and 5 mg of levamlodipine maleate tablets with an anticipated dosage regimen of once daily.

Name of Active Ingredient

Levamlodipine, the (S)amlodipine

Reference Therapy, Dosage and Mode of Administration

Amlodipine Besylate Tablet (NORVASC[®] from Pfizer Inc.)

Study Center

Collaborative Neuroscience Network, LLC (CNS)

[name]

[name]

Principal Investigator

[name]

Objectives

The objectives of this study are (1) to assess the relative bioavailability (BA) of a single oral dose of either 5 mg of Levamlodipine Maleate Tablets from CSPC or 10 mg of Amlodipine Besylate Tablet (NORVASC[®]) from Pfizer Inc. under fasting condition in male and female healthy subjects; and (2) to evaluate food effect on the PK profile of Levamlodipine Maleate Tablets from CSPC.

Study Design

This study consists of 2 parts:

Part 1 will be a randomized, open-label, single-dose, two-way crossover study to assess the relative BA of levamlodipine maleate tablets from CSPC (Test) versus Amlodipine Besylate Tablet NORVASC[®] from Pfizer Inc. (Reference) after a single oral administration under fasted conditions in male and female healthy subjects. Approximately 32 healthy subjects will be enrolled in the US to obtain 27 completed subjects.

Eligible subject will be randomized to receive one of two treatment sequences (RT or TR; R=10 mg of NORVASC[®] and T=5 mg of levamlodipine maleate tablets) according to a randomization schedule prepared prior to the start of the study. All study drugs will be administered following an overnight fast for approximately 10 hours.

Eligible subjects will be admitted to the clinical research center (CRU) within 24 hours before baseline assessments in Period One and will stay at the CRU for 3 nights. A single dose of study drug should be taken orally with 240 ml (about 8 fluid ounces) of water at site after being fasted overnight, and meal will be allowed around 1 hour after dosing. Subjects should return to the CRU on Days 4 till 8 to provide PK samples and to receive study assessments. Serial blood samples will be obtained at defined time points for 7 days after dosing in each treatment for the measurement of plasma (S)amlodipine and (R)amlodipine concentrations.

After a wash-out period for at least 14-days since the last dosing, subjects will enter into Period Two to receive alternative reference or test drug. Thus, subjects who receive levamlodipine treatment in Period One will now receive NORVASC[®] treatment in Period Two, while subjects who receive NORVASC[®] treatment in Period One will now receive levamlodipine treatment in Period Two. The same procedure will be performed at approximately same time points as noted for Period One.

Part 2 will be a single-arm, open-label, single-dose phase to assess food effect on the PK profile of levamlodipine maleate tablets from CSPC. Subjects who have completed Part 1 will be rolled over to Part 2 after a wash-out period for at least 14-days since the last dosing. Subjects will receive a single oral administration of study drug under a high-fat / high-calorie meal that should derive approximately 150, 250 and 500-600 calories from protein, carbohydrate and fat, respectively.

Following an overnight fast for approximately 10 hours, subjects should start the

recommended meal 30 minutes prior to administration of study drug. Study subjects are to eat this meal in 30 minutes or less. The study drug should be administered with 240 mL (about 8 fluid ounces) of water immediately after the meal. No food should be allowed for at least 4 hours post-dose. Water can be allowed as desired except the one-hour period before and after drug administration. Subjects should receive standardized meals scheduled at approximately same time in each period of the study.

Subjects will be admitted to the CRU within 24 hours before drug administration and will stay at the CRU for 3 nights. Subjects should return to the CRU on Days 4 till 8 to provide PK samples and to receive study assessments. Serial blood samples will be obtained at defined time points for the measurement of plasma (S)amlodipine and (R)amlodipine concentrations.

Safety and tolerability will be monitored during the study.

Methodology

PK

A total of 23 blood samples will be collected at the following time points: within 30 min prior to dosing and at 1, 2, 3, 4, 5, 6, 7, 8, 9, 10, 11, 12, 14, 16, 24, 36, 48, 72, 96, 120, 144, and 168 hours after each dosing.

Each plasma sample prepared from blood PK sample will be divided into two equal parts, one as primary PK sample and one as back-up PK sample. Plasma concentrations of (S)amlodipine and (R)amlodipine will be measured with validated methods under GLP.

The plasma concentration time data for (S)amlodipine and (R)amlodipine will be analyzed using non-compartmental methods. Actual dosing and sampling times will be used for analyses. The primary PK parameters of interest are: C_{max} , t_{max} , t_{lag} , $t_{1/2}$, λ_z , MRT_{inf}, AUC_{last}, AUC_{inf}, AUC_{extrap}, Cl/F and V_d/f. Additional parameters may be estimated and reported, as appropriate.

Safety

Safety assessments will include the summaries of adverse events (AEs), vital signs, laboratory findings, 12-lead electrocardiography (ECG), and physical examination findings at various time points during the study.

Planned Subject Number

The planned total subject number for Part 1 is about 32 healthy volunteers in order to obtain 27 completed subjects. Subjects who have completed Part 1 will be rolled over to Part 2 to assess food effect on the PK profile of levamlodipine maleate tablets from CSPC.

Subject Selection Criteria

Inclusion Criteria

To participate in the study, subjects must meet all the following eligibility criteria at screening or admission:

- 1. Are capable of giving informed consent and complying with study procedures;
- 2. Are between the ages of 18 and 45 years old, inclusive;
- 3. Women of childbearing potential (WOCBP) must have a negative pregnancy test at Screening and be practicing a medically acceptable method of contraception with an annual failure rate of less than 1% during the study and 60 days after discontinuation of study treatment. Women are considered not childbearing potential if they are > 1 year postmenopausal or surgically sterile (ie, hysterectomy, bilateral oophorectomy, or bilateral salpingectomy tubal ligation). If serum β HCG is the standard of care, then this value can be used to determine eligibility
- 4. Considered healthy by the Principal Investigator, based on a detailed medical history, full physical examination, clinical laboratory tests, 12-lead ECG and vital signs;
- 5. Nonsmoker, defined as not having smoked or used any form of tobacco in more than 6 months before screening;
- 6. Body mass index (BMI) of 19 to 30 kg/m² inclusive and body weight not less than 50 kg;
- 7. Willing and able to adhere to study restrictions and to be confined at the clinical research center.

Exclusion Criteria

Subjects will be excluded from study entry if any of the following exclusion criteria are present at screening or admission:

- 1. Clinically significant history of gastrointestinal, cardiovascular, musculoskeletal, endocrine, hematologic, psychiatric, renal, hepatic, bronchopulmonary, neurologic, immunologic, lipid metabolism disorders, or drug hypersensitivity;
- Subjects with a mean systolic blood pressure of three measurements >140 mmHg, or a mean diastolic blood pressure of three measurements >90 mmHg at screening. Blood pressure will be measured at sitting position;
- 3. Known or suspected malignancy;
- 4. Positive blood screen for human immunodeficiency virus (HIV), or hepatitis B surface antigen (HBsAg), or hepatitis C virus (HCV);
- 5. A history of seizure. However, a history of febrile seizure is allowed;
- 6. Positive pregnancy test result, or plan to become pregnant if female;
- 7. A hospital admission or major surgery within 30 days prior to screening;

- 8. Participation in any other investigational drug trial within 30 days prior to screening;
- 9. DSM-V substance use disorders within 6 months prior to screening;
- 10. A positive result for alcohol or drugs of abuse at screening or admission;
- 11. Tobacco use within 6 months prior to screening;
- 12. An unwillingness or inability to comply with food and beverage restrictions during study participation;
- 13. Donation or blood collection of more than 1 unit (approximate 450 mL) of blood (or blood products) or acute loss of blood during the 90 days prior to screening;
- 14. Use of prescription or over-the-counter (OTC) medications, and herbal medicines (including St John's Wort, herbal teas, garlic extracts) within 14 days prior to dosing;
- 15. A history of suicide attempt in the past 12 months and/or seen by the investigator as having a significant history of risk of suicide or homicide;
- 16. A history of intolerance or hypersensitivity to amlodipine or any excipients;
- 17. An unwillingness of male participants to use appropriate contraceptive measures if engaging in sex intercourse with a female partner of childbearing potential during the study and 60 days after discontinuation of study treatment. Sexual intercourse with pregnant or lactating women is prohibited.

Duration of Study

The total duration of the study for each completed subject is about 2 months, including about 44 days for Part 1 (up to 21 days for screening, 14 days for Period One before cross-over and 9 days for Period Two after cross-over) and about 14 days for Part 2 (5 days before dosing and 9 days after dosing).

Statistical Methods

PK

All the PK parameters and baseline subject characteristics will be summarized using descriptive statistics. The following PK parameters for plasma (S)amlodipine and (R)amlodipine concentrations will be compared between the study treatments by analysis of variance (ANOVA) including subject, treatment, and sequence effects in the model. Statistical significance will be tested at the 0.05 level (2-sided):

- AUC_{0-t} (Area under the concentration-time curve up to the time of the last quantifiable concentration)
- $AUC_{0-\infty}$ (Area under the concentration-time curve extrapolated to infinity)
- C_{max}
- t_{max}

• t_{1/2}

AUC_{0-t}, AUC_{0- ∞} and C_{max} will present estimates of extent and rate of absorption. t_{max} will be compared between treatments using the Wilcoxon-Singed Ranks test.

Relative bioavailability of Levamlodipine Maleate Tablets (T) and NORVASC[®] (R) will be determined based on AUC_{0-t}, AUC_{0-inf} and C_{max} of (S)amlodipine. The 90% confidence intervals (CIs) on the ratio of test to reference drugs will be calculated. Log-transformed PK parameters AUC_{0-t}, AUC_{0-inf} and C_{max} will be analyzed using ANOVA including terms for sequence, treatment, and period as fixed effects, and subject nested within sequence as a random effect. Bioequivalence limits will be 80–125%.

The PK parameters for plasma (S)amlodipine and (R)amlodipine concentrations will be compared within treatment of either Levamlodipine Maleate Tablets or NORVASC[®] to determine possible conversion of the 2 isomers in vivo.

Food effect will be evaluated based on AUC_{0-t} , AUC_{0-inf} and C_{max} of (S)amlodipine and will be determined by the changes of log-transformed PK parameters under fasting conditions and fed conditions.

Safety

Safety data will be summarized using descriptive statistics for all subjects who receive study drugs.

AEs will be coded using the MedDRA Dictionary, listed by subject and summarized frequency (number) for each treatment. Prior and concomitant medications will be coded using the World Health Organization (WHO) Drug Dictionary, and listed by reported term and Anatomical Therapeutic Class classification.

Any abnormal findings in physical examination and clinical laboratory tests will be summarized by treatment. Change from baseline will be calculated for clinical laboratory tests. For ECGs, the frequency (number) of clinically significant findings will be reported and summarized by treatment.

2. LIST OF ABBREVIATIONS

The following abbreviations	and specialist term	s are used in this study protocol.
0	······································	

Abbreviation	Term
AE	Adverse event
ALT	Alanine aminotransferase
ANOVA	Analysis of variance
AST	Aspartate aminotransferase
AUC	Area under curve
AUCinf	Area under the analyte concentration-time curve from time 0 and extrapolated to infinite time, total exposure
AUC _{last}	Area under the analyte concentration time curve from time 0 to last quantifiable concentration
BMI	body mass index
BP	Blood pressure
BUN	Blood urea nitrogen
C _{max}	Maximum concentration
Con med	Concomitant medication
CFR	Code of Federal Regulations
CI	Confidence interval
CRF	Case report form
CRO	Contract research organization
CRU	Clinical research unit
CSPC Pharma	CSPC Pharmaceutical Co., Ltd.
ECG	Electrocardiography
FDA	Food and Drug Administration
GCP	Good Clinical Practice
GGT	Gamma-glutamyl-transferase
Hct	Hematocrit
HCV	Hepatitis C virus
Hgb	Hemoglobin
HIV	Human immunodeficiency virus

Abbreviation	Term			
IB	Investigational brochure			
ICF	Informed consent form			
ICH	International Conference on Harmonisation			
IEC	Independent Ethics Committee			
IRB	Institutional Review Board			
LC-MS/MS	Tandem mass spectrometric detection			
LDH	Lactate dehydrogenase			
MedDRA	Medical Dictionary for Regulatory Activities			
NOAEL	No observable adverse effect level			
ОТС	Over the Counter			
PHI	Protected health information			
PK	Pharmacokinetic(s)			
R	Reference product			
RBC	Red blood cell			
SAE	Serious adverse event			
SAD	Single ascending dose			
SDV	Source document verification			
t _{1/2}	Half life			
Т	Test product			
TEAE	Treatment-emergent AEs			
t _{max}	Time of maximum observed plasma concentration			
WHO	World Health Organization			

3. INTRODUCTION

Amlodipine is a third-generation calcium channel blocker that prevents calcium from entering myocardial cells and vascular smooth muscle cells, and thus has antihypertension effect. Amlodipine in the besylate salt form was developed by Pfizer Laboratories and was approved as NORVASC 2.5 mg, 5.0 mg, and 10.0 mg Tablets by the U.S. FDA for the treatment of hypertension in 1992 (NDA No. 019787). Generic equivalents of NORVASC have been marketed globally since 2007.

Amlodipine is a 1:1 racemic mixture of S-amlodipine (the levorotatory L-form) and Ramlodipine (the dextrorotatory D-form). S-amlodipine is the pharmacologically active moiety in racemic amlodipine. Clinically, S-amlodipine, at half the dose of amlodipine (2.5 mg vs. 5 mg, respectively), has been found to be equivalent to racemic amlodipine in efficacy, safety, and tolerability, with less edema, in patients with mild to moderate hypertension.

Levamlodipine maleate tablets 2.5 mg, a purified S-amlodipine tablet formulation, was approved for marketing in China in 2003 (Drug Code 86902770002300) for the treatment of hypertension and angina. Levamlodipine maleate tablets 2.5 mg are marketed under the trade name Xuanning® in China.

4. STUDY OBJECTIVES

The objectives of this study are (1) to assess the relative bioavailability (BA) of a single oral dose of either 5 mg of Levamlodipine Maleate Tablets from CSPC or 10 mg of Amlodipine Besylate Tablet (NORVASC[®]) from Pfizer Inc. under fasting condition in male and female healthy subjects; and (2) to evaluate food effect on PK profile of Levamlodipine Maleate Tablets.

5. INVESTIGATIONAL PLAN

5.1. Study Design

This study consists of 2 parts. **Part 1** will be a randomized, open-label, single-dose, two-way crossover study to assess the relative BA of 5 mg of levamlodipine maleate tablets from CSPC (Test Product) versus 10 mg of Amlodipine Besylate Tablet NORVASC[®] from Pfizer Inc. (Reference Product) after a single oral administration under fasted conditions in male and female healthy subjects. Approximately 32 healthy volunteers will be enrolled for Part 1 to obtain 27 completed subjects.

Part 2 will be a single-arm, open-label, single-dose phase to assess food effect on the PK profile of levamlodipine maleate tablets from CSPC. Subjects who have completed Part 1 will be rolled over to Part 2 after a wash-out period for at least 14-days since the last dosing. Subjects will

receive a single oral administration of 5 mg levamlodipine maleate tablets from CSPC under a high-fat/high-calorie meal that should derive approximately 150, 250 and 500-600 calories from protein, carbohydrate and fat, respectively.

5.2. Study Methods

The detailed timing and scheduling for **Part 1** are shown in Table 5-1, Table 5-2. Eligible subject will be randomized to receive one of two treatment sequences (RT or TR; R=10 mg of NORVASC[®] and T=5 mg of levamlodipine maleate tablets) according to a randomization schedule prepared prior to the start of the study. All study drugs will be administered following an overnight fast for approximately 10 hours.

Eligible subjects will be admitted to the clinical research center (CRU) within 24 hours before baseline assessments in Period 1 and will stay at the CRU for 3 nights. A single dose of study drug should be taken orally with 240 ml (about 8 fluid ounces) of water at site after being fasted overnight, and meal will be allowed around 1 hour after dosing. Subjects should return to the CRU on Days 4 till 8 to provide PK samples and to receive study assessments. Serial blood samples will be obtained at defined time points within 7 days after dosing in each treatment for the measurement of plasma (S)amlodipine and (R)amlodipine concentrations.

After a wash-out period for at least 14-days since the last dosing, subjects will enter into Period 2 to receive alternative reference or test drug. Thus, subjects who receive levamlodipine treatment in Period 1 will now receive NORVASC[®] treatment in Period Two, while subjects who receive NORVASC[®] treatment in Period One will now receive levamlodipine treatment in Period 2. The same procedure will be performed at approximately same time points as noted for Period 1.

The detailed timing and scheduling for **Part 2** are shown in Table 5-3. Following an overnight fast for approximately 10 hours, subjects will eat a high-fat/high-calorie. This meal should derive approximately 150, 250 and 500-600 calories from protein, carbohydrate and fat, respectively.

Subjects should start the recommended meal 30 minutes prior to administration of study drug, and finish this meal in 30 minutes or less. The study drug should be administered with 240 mL (about 8 fluid ounces) of water immediately after the meal. No food should be allowed for at least 4 hours post-dose. Water can be allowed as desired except the 1-hour period before and after drug administration.

Subjects will be admitted to the clinical research center (CRU) within 24 hours before drug administration and will stay at the CRU for 3 nights. Subjects should return to the CRU on Days 4 till 8 to provide PK samples and to receive study assessments. Serial blood samples will be obtained at defined time points for the measurement of plasma (S)amlodipine and (R)amlodipine concentrations.

Safety and tolerability will be monitored during the study.

	Screening		Clinical Resear	Clinical Visits						
Day	(Day -21 to -1)	Day 0 ¹ (Baseline)	Day 1 (Dosing)	Day 2	Day 3	Day 4	Day 5	Day 6	Day 7	Day 8
Informed consent	X									
Medical history	X									
Physical examination ²	Х									Х
Vital signs ³	X	Х	Х	X	Х	Х	Х	Х	Х	Х
12-lead ECG	X	X ⁴								Х
Clinical safety tests	X ⁵	Х								Х
Drug/alcohol test	Х	Х								Х
Pregnancy test ⁶	Х	Х								
Admission to CRU		Х								
Randomization			Х							
Dose administration			Х							
PK blood samples ⁷			Х	X	Х	Х	Х	Х	Х	Х
AE & ConMed		Х	Х	X	Х	Х	Х	Х	Х	Х
Discharge from CRU					Х					

 Table 5-1.
 Schedule of Procedures for Part 1 - Period 1

¹ Baseline.

² Including body weight and height at screen only.

³ Complete vital sign measurements at screening visit, Day 0 and 0, 24, 96 and 168 hours after dosing. Blood pressure and heart rate only at other time points. Three measurements

of blood pressure at screening visit and a single measurement at other time points.

⁴ Three ECG tests with 3 min interval in between on Day 0. The means of the three ECG tests will be used as baselines.

⁵ HIV, hepatitis B & C screen test at screening visit only.

⁶ Serum test at screening and urine test on Day 0 for females of childbearing potential only.

⁷ Pharmacokinetic blood samples will be collected at the following time points: Pre-dose (within 30 min prior) and at 1, 2, 3, 4, 5, 6, 7, 8, 9, 10, 11, 12, 14, 16, 24, 36, 48, 72, 96,

120, 144, and 168 hours after dosing (acceptable windows: ± 2 min for 0 to 2-hr post dose period and ± 5 min thereafter)

AE = adverse event; ConMed = concomitant medications; CRU = clinical research unit; ECG = electrocardiogram; PK = pharmacokinetics.

Confidential

	Wash-out	Clini	ch Unit (Cl	Clinical Visits						
Day	At least 14 days since the last dosing	Day 0 (Admission)	Day 1 (Dosing)	Day 2	Day 3	Day 4	Day 5	Day 6	Day 7	Day 8
Admission to CRU		Х								
Cross-over of treatment		Х								
Physical examination		Х								Х
Vital signs 1		Х	Х	Х	Х	Х	Х	Х	Х	Х
12-lead ECG		Х								Х
Clinical safety tests		Х								Х
Drug/alcohol test		Х								Х
Pregnancy test ²		Х								Х
Dose administration			Х							
PK blood samples ³			Х	Х	Х	Х	Х	Х	Х	Х
AE & ConMed		Х	Х	Х	Х	Х	Х	Х	Х	Х
Discharge from CRU					Х					

Table 5-2. Schedule of Procedures for Part 1 - Period 2

¹ Complete vital sign measurements at 0, 24, 96 and 168 hours after dosing. Blood pressure and heart rate only at other time points. Three measurements of blood pressure at screening visit and a single measurement at other time points.

² Urine test for females of childbearing potential only.

³ Pharmacokinetic blood samples will be collected at the following time points: Pre-dose (within 30 min prior) and at 1, 2, 3, 4, 5, 6, 7, 8, 9, 10, 11, 12, 14, 16, 24,

36, 48, 72, 96, 120, 144, and 168 hours after dosing (acceptable windows: $\pm 2 \min$ for 0 to 2-hr post dose period and $\pm 5 \min$ thereafter)

AE = adverse event; ConMed = concomitant medications; CRU = clinical research unit; ECG = electrocardiogram; PK = pharmacokinetics.

	Wash-out	Clin	Clinical Research Unit (CRU)				h Unit (CRU) Clinical Visits			
Day	At least 14 days since the last dosing	Day 0 (Admission)	Day 1 (Dosing)	Day 2	Day 3	Day 4	Day 5	Day 6	Day 7	Day 8 ⁵
Admission to CRU		Х								
Physical examination		Х								Х
Vital signs ¹		Х	Х	Х	Х	Х	Х	Х	Х	Х
12-lead ECG		Х								Х
Clinical safety tests		Х								Х
Drug/alcohol test		Х								Х
Pregnancy test ²		Х								Х
High-fat/calorie meal ³			X							
Dose administration			X							
PK blood samples ⁴			X	Х	Х	X	Х	Х	Х	Х
AE & ConMed		X	X	Х	X	X	Х	Х	X	X
Discharge from CRU					X					

 Table 5-3.
 Schedule of Procedures for Part 2 (Food Effect)

¹ Complete vital sign measurements on Day 0 and 0, 24, 96 and 168 hours after dosing. Blood pressure and heart rate only at other time points.

² Urine test for females of childbearing potential only.

³ The meal should be started 30 minutes prior to administration of study drug, and finished in 30 minutes or less

⁴ Pharmacokinetic blood samples will be collected at the following time points: Pre-dose (within 30 min prior) and at 1, 2, 3, 4, 5, 6, 7, 8, 9, 10, 11, 12, 14, 16, 24,

36, 48, 72, 96, 120, 144, and 168 hours after dosing (acceptable windows: $\pm 2 \min$ for 0 to 2-hr post dose period and $\pm 5 \min$ thereafter)

⁵ End-of the study or early termination.

AE = adverse event; Con Med = concomitant medications; CRU = clinical research unit; ECG = electrocardiogram; PK = pharmacokinetics.

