7. STUDY PROCEDURES

The following sections describe in detail all study procedures. The schedule of procedures is presented in Table 5-1, Table 5-2, Table 5-3.

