7.1.2. Baseline (Day 0)

Subjects will be admitted to the CRU on Day 0 and remain sequestered at the CRU until the collection of the PK sample of 48 hours after dosing.

On arrival at the clinical research unit, all subjects will undergo the following assessments:

- Vital signs including blood pressure, heart rate, respiratory rate and temperature
- Three 12-lead ECGs will be recorded with 3-min interval at this visit. The means of the three ECGs will be used as the baselines.
- Overnight fasting blood sample collection for safety tests
- Drug/alcohol test
- Urine pregnancy test for females of childbearing potential
- Admission to the CRU for eligible subjects
- Assessment of AEs and concomitant medications

Enrolled patients will be fasted from 10 pm the day prior to dosing until approximately 4 hours after administration the next day (dosing day). Water intake will be permitted until 6 am of the dosing day.

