7.1.3. Dosing (Day 1)

The following assessments and procedures will be performed and documented at this visit:

- Vital signs. Prior to dosing, blood pressure, heart rate, respiratory rate and temperature will be measured. For all other time points, only blood pressure and heart rate will be measured
- Randomization to treatment
- Administration of study drug. Dose will be administered orally with 240 mL of room temperature water in an upright position under fasting conditions at approximately 8 am. Subjects should not drink water and need to maintain an upright position for 2 hours after the administration of the study drug. Lunch will be served at approximately 4 hours after the administration and dinner as the standard meal at approximately 10 hours post dose. If needed, evening snack can be provided. Time of administration will be documented for both study drug and meals.
- Pharmacokinetic blood samples will be collected at the following time points: Pre-dose (within 30 min prior) and at 1, 2, 3, 4, 5, 6, 7, 8, 9, 10, 11, 12, 14, 16, 24, 36, 48, 72, 96, 120, 144, and 168 hours after dosing (acceptable windows: ± 2 min for 0 to 2-hr post dose period and ± 5 min thereafter)
- Assessment of AEs and concomitant medications.

All doses of study drug will be administered orally under fasting conditions at approximately 8 am on the day of dosing. Subjects will be closely supervised and within sight of study personnel within 8 hours after dosing. Actual times for dosing, each assessment and meals (start times for meals on the day of dosing) must be recorded. Any deviations from the protocol-specified administration schedule will also be documented.

7.1.4. Days 2 through 7

The following assessments and procedures will be performed and documented.

- Daily vital sign measurements
- Pharmacokinetic blood sample collections (acceptable windows: ± 5 min). See PK timepoints in section 7.1.3 and footnote of Table 5-1
- Assessment of AEs and concomitant medications daily
- Discharge from CRU on Day 3 after the 48-hour after dosing PK sample is obtained. Subjects will be remined to return to CRU at defined time to provide PK sample and to receive study assessments

7.1.5. Day 8

The following assessments and procedures will be performed and documented.

- Physical examination
- Vital sign measurements

- A single 12-lead ECG
- Overnight fasting blood sample collection for safety tests
- Drug and alcohol test

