7.3.2. Dosing (Day 1)

The following assessments and procedures will be performed and documented at this visit:

- Vital signs. Prior to dosing, blood pressure, heart rate, respiratory rate and temperature will be measured. For all other time points, only blood pressure and heart rate will be measured
- High-fat/high-calorie meal. Following an overnight fast of at least 10 hours, subjects should start the recommended meal 30 minutes prior to administration of the drug product. Study subjects should eat the a high-fat / high-calorie meal in 30 minutes or less. This meal should derive approximately 150, 250 and 500-600 calories from protein, carbohydrate and fat, respectively. Subjects should receive standardized meals scheduled at the same time in each period of the study.
- Administration of study drug. Dose will be administered orally with 240 mL of room temperature water in an upright position under using meal conditions at approximately 8 am. No food should be allowed for at least 4 hours post-dose. Water can be allowed as desired except for one hour before and after drug administration. Subjects should receive standardized meals scheduled at the same time in each period of the study.
- Pharmacokinetic blood samples will be collected at the following time points: Pre-dose (within 30 min prior) and at 1, 2, 3, 4, 5, 6, 7, 8, 9, 10, 11, 12, 14, 16, 24, 36, 48, 72, 96, 120, 144, and 168 hours after dosing (acceptable windows: ± 2 min for 0 to 2-hr post dose period and ± 5 min thereafter)
- Assessment of AEs and concomitant medications.

Subjects will be supervised and within sight of study personnel within 8 hours after dosing. Actual times for dosing, each assessment and meals (start times for meals on the day of dosing) must be recorded. Any deviations from the protocol-specified administration schedule will also be documented.

7.3.3. Days 2 through 7

The following assessments and procedures will be performed and documented.

- Daily vital sign measurements
- Pharmacokinetic blood sample collections (acceptable windows: ± 5 min). See PK timepoints in section 7.3.2 and footnote of Table 5-3
- Assessment of AEs and concomitant medications daily
- Discharge from CRU on Day 3 after the 48-hour after dosing PK sample is obtained. Subjects will be remined to return to CRU at defined time to provide PK sample and to receive study assessments

7.3.4. Day 8

The following assessments and procedures will be performed and documented.

- Physical examination

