1 INTRODUCTION

This statistical analysis plan (SAP) describes the final statistical analysis for subject information and safety data to be done for the study entitled "A Randomized, Open-label, Single-Dose, Two-Way Crossover Study to Assess the Relative Bioavailability of 5 mg of Levamlodipine Maleate Tablets versus 10 mg of Amlodipine Besylate Tablet (NORVASC® from Pfizer Inc.) in Healthy Subjects Followed by a Phase to Study Food Effect on the PK Profile of Levamlodipine" (V2.0 21MAY2018). All planned PK analyses will be described in a separate PK analysis plan. Mock shells are also produced as a separate working document to facilitate programming of Tables, Figures, and Listings (TFLs) according to finalized SAP. The SAP is to be interpreted in conjunction with the protocol, and supersedes the statistical considerations identified in the protocol. If the final clinical study report contains changes to any planned statistical analyses, the justification for any such differences will be fully documented in the CSR.

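### Part 1 post-dose food: the Synopsis, Protocol 5.2 and SAP 1.2 permit a meal at about 1 hour, but Protocol 7.1.2 continues the fast to about 4 hours, and nothing says which text governs

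*Protocol*

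**What the plan says.** **The earlier-meal text (Part 1).** After describing the overnight fast and the dose with water, Protocol 5.2 says a "meal will be allowed around 1 hour after dosing". The same words stand in the Synopsis (Study Design, Part 1) and in SAP 1.2. None of the three limits the permission to a snack, a drink or one period.

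**The longer-fast text (Part 1).** Protocol 7.1.2 has subjects "fasted from 10 pm the day prior to dosing until approximately 4 hours after administration". Protocol 7.2 repeats the procedure at the same time points in Period Two. Protocol 7.1.3 states "Lunch will be served at approximately 4 hours after the administration", followed by dinner at about 10 hours, and 7.2.2 gives the same schedule for Period Two. Both sections also bar drinking water for 2 hours after the dose.

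**Part 2 (fed).** The Synopsis, 5.2 and 7.3.2 each state: "No food should be allowed for at least 4 hours post-dose". The Synopsis adds: "Subjects should receive standardized meals scheduled at approximately same time in each period of the study". Section 7.3.2 has a near-identical sentence: "Subjects should receive standardized meals scheduled at the same time in each period of the study".

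**On precedence.** Section 7 opens with "The following sections describe in detail all study procedures". SAP 1 says that the SAP "supersedes the statistical considerations identified in the protocol". SAP Section 7 lists only the randomization wording as a change from the protocol. SAP Listing 16.2.6.3 is titled for a pre-dose meal and for lunch and dinner after dosing.

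**The concern.** Fasting is the condition under which Objective 1 is defined, and how long it lasts after dosing is part of that condition. Coordinators working from 5.2 and from 7.1.2 would feed subjects at different times, and each would be in breach of the other section. The plan therefore does not say what counts as a deviation on this point.

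The Part 1 levamlodipine profile is used twice. It is compared with NORVASC for relative bioavailability, on AUC and Cmax against limits of 80–125%. It is also the fasting side of the food-effect comparison in Protocol 12.3. The second use is the more exposed. Part 2 is a single-arm phase with its own post-dose food rule, so any difference in post-dose meal timing between Part 1 and Part 2 is carried into the food-effect estimate together with the test meal.

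**Working it through.** No power or sample-size figure is involved. The check compares the texts and does clock arithmetic. All times are approximate, because the documents use approximate wording.

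**Inputs**
- Dosing time: about 08:00 (Protocol 7.1.3, 7.2.2, 7.3.2).
- Start of fast: 22:00 the evening before (7.1.2), which is 10 h before dosing.
- Part 1 food, rule A: 1 h after dosing (Synopsis, 5.2, SAP 1.2).
- Part 1 food, rule B: 4 h after dosing (7.1.2).
- Part 2 food: not before 4 h after dosing (Synopsis, 5.2, 7.3.2).

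**Step 1. The two Part 1 rules**

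| | Rule A | Rule B |
|---|---|---|
| First post-dose food | 08:00 + 1 h = 09:00 | 08:00 + 4 h = 12:00 |
| Total fast | 10 h + 1 h = 11 h | 10 h + 4 h = 14 h |

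The gap is 4 h − 1 h = 3 h, whatever the clock time of dosing. Rule A would place food around the 1-hour sample and before the 2-, 3- and 4-hour samples. Rule B would place it around the 4-hour sample.

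**Step 2. Which passages conflict directly**
- Rule A against 7.1.2: a direct conflict. A meal permitted at 1 h falls inside a fast that runs to about 4 h, and approximate wording cannot absorb 3 h. Section 7.2 extends this to Period Two.
- Rule A against 7.1.3 and 7.2.2: a poor fit, but not a prohibition. Lunch at about 4 h is the first post-dose meal they list, and water may not be drunk for 2 h, a window that would contain a 1-hour meal. Neither section itself forbids earlier food.
- Rule A against SAP Listing 16.2.6.3: also a poor fit. The listing's title has no place for a separate 1-hour meal.

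**Step 3. Earliest post-dose food, Part 2 minus Part 1**
- Under rule A: at least 4 h − 1 h, so at least about 3 h later in Part 2.
- Under rule B: at least 4 h − 4 h, so at least about 0 h. The two can coincide, but the Part 2 wording is a lower bound and does not guarantee it.

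**Step 4. Precedence**
The opening of Section 7 claims detail; it does not say that Section 7 overrides other sections. The SAP's claim to supersede is confined to statistical considerations, and SAP 1.2 repeats rule A in a design recap. Neither settles the matter.

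**The case against.** The best case against the point is that the operational answer is already visible. Section 7 is the detailed procedures section and agrees with itself for Part 1. The planned listing names only lunch and dinner after dosing. The 1-hour wording is one sentence repeated in three design summaries, one of them in a SAP confined to subject information and safety. There is a single site, and meal start times on the dosing day must be recorded, so mixed practice is less likely and would be visible. All of that stands, and it lowers the risk. It does not remove the contradiction, because the 1-hour sentence remains in 5.2, and a recorded meal time shows what happened without showing which instruction applied.

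A reader might infer three stronger things that the documents do not support:
- **That 7.1.3 and 7.2.2 are independent prohibitions of a 1-hour meal.** They schedule lunch. The prohibition comes from 7.1.2, carried forward by 7.2.
- **That the Synopsis contradicts itself because Part 2 bars food for at least 4 hours.** Different parts may have different rules. A conflict arises only if the sentence on meal times in each period spans both parts. That reading is plausible: Part 2 has one dosing occasion, and SAP 2.3 counts three treatment periods. But the protocol numbers periods only within Part 1, so it remains an interpretation.
- **That the 4-hour text would make meal timing equal in Parts 1 and 2.** It would allow this without ensuring it.

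**Conclusion.** The contradiction is real and should be resolved before dosing. It affects both Part 1 periods and amounts to about 3 hours in the time of first post-dose food. Under the 1-hour text, fasted and fed conditions would differ by at least about 3 hours in earliest post-dose food, in addition to the test meal. Under the 4-hour text, the lower bound on that difference is about zero. If the sentence on meal times covers both parts, that requirement is engaged as well.

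A reader might go further and infer that the bioequivalence result is compromised. The documents do not support that. If one rule is applied uniformly to both products and both periods, the test-to-reference ratio remains estimable. Nor do the documents give any figure from which the size or direction of an effect on Cmax, tmax or AUC could be derived, for either comparison.

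The conclusion rests on the texts as written and on dosing at about 8 am for the clock times; the 3-hour gap does not depend on the hour of dosing. It takes no position on which meal timing is right.

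**What to change.** Before dosing, reconcile the Synopsis, Protocol 5.2 and SAP 1.2 with Protocol 7.1.2, 7.1.3 and 7.2.2, so that one Part 1 post-dose meal rule is stated, identical for levamlodipine and NORVASC and for both periods. In the same amendment, say how that rule relates to the Part 2 food restriction, and whether the sentences on meal times in the Synopsis and 7.3.2 cover Part 1 as well as Part 2. If a difference between the parts is intended, state it as deliberate. The choice of timing belongs to the sponsor and the investigator.

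The cost is a wording amendment to the protocol and to SAP 1.2. It adds no subjects, visits or samples.
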